6. EXPERIMENTAL DESIGN

This will be a 1:1 randomized, open-label, multi-institution phase II trial designed to evaluate the immunological and clinical effect of one versus two DNA vaccines, used as T-cell activating therapies, and given concurrently with pembrolizumab. Study arms will be defined as follows:

Course 1:

Arm 1: 100 μg pTVG-HP administered intradermally (i.d.) days 1, 8 + 200 mg

pembrolizumab IV day 1 of 21-day cycles x 8 cycles

Arm 2: 100 μg pTVG-AR i.d days 1, 8 + 200 mg pembrolizumab IV day 1 of 21-day cycles,

for cycles 1, 2, 5 and 6 alternating with

100 μg pTVG-HP i.d. days 1, 8 + 200 mg pembrolizumab IV day 1 of 21-day

cycles, for cycles 3, 4, 7 and 8

Patients who have not come off trial at the end of cycle 8 (month 6) will continue to receive pembrolizumab at 3-week intervals, up to a total of 2 years of treatment (32 cycles), or until evidence of radiographic progression. If prior to 2 years, and in the absence of radiographic progression, patients with rise in PSA (25% over month 6 value and with minimum rise of 2 ng/mL) will resume vaccination in follow-on courses:

Arm 1: 100 μg pTVG-HP i.d. days 1, 8 + 200 mg pembrolizumab IV day 1 of 21-day cycles

x 4 cycles

Arm 2: 100 μg pTVG-AR i.d days 1, 8 + 200 mg pembrolizumab IV day 1 of q 21-day

cycles, for two cycles followed by

100 µg pTVG-HP i.d. days 1, 8 + 200 mg pembrolizumab IV day 1 in 21-day

cycles, for two cycles

Study Arm Assignment and Toxicity Assessment

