- 2. Blood draw for CBC, chemistry panel, serum PSA and PAP (can be performed up to 3 days prior to this visit)
- 3. Pembrolizumab 200 mg dose, administered intravenously over 30 minutes
- 4. NOTE: Every 4 cycles (i.e. continuing every 12 weeks) at cycles 13, 17, 21, 25, and 29): CT scan of abdomen and pelvis (CT of chest as clinically indicated), bone scintigraphy. Scans can be performed +/- 7 days from day of visit.

5. NOTE: For cycles 13 and 17: 10 ml peripheral blood (red-top tubes) for sera to evaluate antibody responses, and 100 ml peripheral blood (green-top heparinized tubes) for T-cell response evaluation (can be performed +/- 7 days of this visit)

If patients are observed in the course of the pembrolizumab alone cycles to have:

- 1) absence of radiographic progression
- 2) evidence of PSA rise (25% increase over value obtained at cycle 9 day 1, and minimum of 2 ng/mL increase)
- 3) this occurs prior to cycle 29

THEN Subjects will undergo 4 vaccine booster cycles in place of the pembrolizumab cycles above, and then resume pembrolizumab alone cycles as above. Immune blood draws (cycles 13 and 17) and CT scans/bone scintigraphy (cycles 13, 17, 21, 25, 29) continue as above.

VACCINE BOOSTER CYCLES

- g. Day 1 (21 +/- 3 days after last cycle day 1)
- 1. Physical examination, including vital signs, symptoms and medications assessment, and ECOG performance score
- 2. Blood draw for CBC, differential and platelets, chemistry panel, PSA and PAP
- 3. Subjects will receive pTVG-HP DNA (Arm 1, or cycles 3 or 4 for Arm 2) or pTVG-AR DNA (cycles 1 or 2 for Arm 2) immunizations intradermally on the deltoid area of the lateral arm (preferentially left arm) with 0.25 mL administered at each of two adjacent sites.
- 4. Following vaccinations, the subjects will be observed for 60 minutes for unanticipated adverse events.
- 5. Pembrolizumab 200 mg dose, administered intravenously over 30 minutes
- 6. Subjects will be observed for additional 30 minutes for unanticipated adverse events.
 - h. Day 8 (7 + / 2 days after day 1)
- 1. Subjects will receive pTVG-HP DNA (Arm 1, or cycles 3 or 4 for Arm 2) or pTVG-AR (cycles 1 or 2 for Arm 2) immunizations intradermally on the deltoid area of the lateral arm (preferentially left arm) with 0.25 mL administered at each of two adjacent sites.
- 2. Following vaccinations, the subjects will be observed for 60 minutes for unanticipated adverse events.

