11. STATISTICAL CONSIDERATIONS

r. Overview

This is a 1:1 randomized, open-label, multi-institution phase II trial designed to evaluate the immunological and clinical effect of one versus two DNA vaccines, used as T-cell activating therapies, and given concurrently with pembrolizumab. The rationale for conducting this trial is summarized in Section 2.

s. Objectives

Primary Objective:

To determine the 6-month progression-free survival rate in patients with metastatic, castration-resistant prostate cancer (mCRPC) treated with pembrolizumab in combination with one versus two DNA vaccines as T-cell activating agents

Secondary Objectives:

- 1. To determine the overall objective response rate (using Prostate Cancer Working Group 3 (PCWG3) criteria)
- 2. To determine the PSA response rate (decline > 50%)
- 3. To determine the median progression-free survival rate
- 4. To determine median duration of PSA and/or objective response in responding individuals
- 5. To determine the overall survival
- 6. To determine whether the development of antigen-specific Th1 immunity elicited with treatment to either antigen (PAP or AR) is associated with PSA response
- 7. To evaluate the safety and tolerability of pTVG-HP DNA vaccine with or without pTVG-AR DNA vaccine and pembrolizumab

Exploratory Objectives:

- 1. To evaluate PAP-specific and AR-specific antibody responses following treatment with pembrolizumab and DNA vaccine(s)
- 2. To determine whether treatment with either sequence elicits immunologic antigen spread to other prostate associated antigens
- 3. To determine whether pre-existing antigen-specific immunity is predictive of immunological or objective clinical response
- 4. To determine, in a subset of patients, whether early changes in bone observed by NaF PET/CT are associated with immunological or objective clinical response, or pathological changes associated with immune-cell infiltration
- 5. To determine second PSA response rates in patients treated in follow-on courses
- 6. To determine whether treatment elicits changes in the gut microbiota composition
- 7. To determine whether changes in gut microbiota are associated with clinical response (PSA decline > 50%)

t. Study Design

The study is designed as a randomized, two-arm, open-label, multi-institution phase 2 trial. Study arms will be defined as follows:

Course 1:

Arm 1: 100 μg pTVG-HP administered intradermally (i.d.) days 1, 8 + 200 mg

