pembrolizumab IV day 1 of 21-day cycles x 8 cycles

Arm 2: 100 μg pTVG-AR i.d days 1, 8 + 200 mg pembrolizumab IV day 1 of 21-day cycles,

for cycles 1, 2, 5 and 6 alternating with

100 µg pTVG-HP i.d. days 1, 8 + 200 mg pembrolizumab IV day 1 of 21-day

cycles, for cycles 3, 4, 7 and 8

Patients who have not come off trial at the end of cycle 8 (month 6) will continue to receive pembrolizumab at 3-week intervals, up to a total of 2 years (32 cycles) of treatment, or until evidence of radiographic progression. If prior to 2 years, and in the absence of radiographic progression, patients with rise in PSA (25% over month 6 value and with minimum rise of 2 ng/mL) will resume vaccination in follow-on courses:

Arm 1: 100 μg pTVG-HP i.d. days 1, 8 + 200 mg pembrolizumab IV day 1 of 21-day cycles

x 4 cycles

Arm 2: 100 μg pTVG-AR i.d days 1, 8 + 200 mg pembrolizumab IV day 1 of q 21-day

cycles, for two cycles followed by

100 µg pTVG-HP i.d. days 1, 8 + 200 mg pembrolizumab IV day 1 in 21-day

cycles, for two cycles

Eligible subjects will be randomly assigned in 1:1 fashion to either Arm 1 or Arm 2.

u. Randomization and Stratification

Eligible patients will be randomized to the two study arms with an allocation ratio of 1:1. The randomization will be stratified by institution and prior treatment (or not) with prior second generation AR targeting agents. Treatment arm assignment will be made by biostatics/investigational pharmacy after a patient has been registered.

v. Sample Size and Power Calculation

The expected 6-months PFS rate in Arm 1 (pTVG-HP DNA vaccine and Pembrolizumab) in this patient population is 20-30%. It is hypothesized that adding pTVG-AR DNA vaccine (Arm 2) will increase the 6-months PFS rate to at least 55%. The following table shows the required sample sizes for detecting various differences in the 6-months PFS rates between the two study arms, assuming 80% power and a one-sided 0.10 significance level. As this is a phase II study, a less stringent significance level of 0.10 rather than the traditional 0.05 level will be used for the primary efficacy evaluation.

Required sample sizes to detect a difference of 20-30% vs. 50-60% in the 6-months PFS rates between arms			
	6-mont	hs PFS rate in	ı Arm 2
6-months PFS rate in Arm 1	0.50	0.55	0.60
0.20	54	42	32
0.25	80	58	44
0.30	124	82	58

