Generalized linear models with a logit link function will be used to evaluate PAP-specific and ARspecific antibody responses following treatment with pembrolizumab and DNA vaccine(s), and to determine whether treatment with either sequence elicits immunologic antigen spread to other prostate associated antigens. Logistic regression analysis will be utilized to determine whether pre-existing antigen-specific immunity is predictive of immunological or objective clinical response. The interaction term between pre-existing antigen-specific immunity status and treatment arm will be included in this model and evaluated. Analogously, a generalized linear model with subject specific random effects will be used to determine whether early changes in bone observed by NaF PET/CT are associated with immunological or objective clinical response, or pathological changes associated with immune-cell infiltration. The number and frequencies of second PSA responses in patients treated in follow-on courses will be summarized in tabular format. The stratified (by randomization strata) Mantel-Haenszel test will be used to compare second PSA response rates between study arms. Bacterial, viral and archeal species loads identified from the bioinformatics analysis of the microbiome samples will be compared between pre- vs. post-treatment assessment using a paired t-test. The false discovery rate will be controlled using the Benjamini-Hochberg False Discovery Rate (FDR) method. Logistic analyses will be conducted to determine whether changes in gut microbiota are associated with clinical response.

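### The between-arm test of second PSA response compares subsets formed after randomization, so its p-value is not a randomized comparison and could be biased in either direction

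*Combined protocol and SAP*

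**What the plan says.** Exploratory objective 5 (Section 11, Objectives) is "To determine second PSA response rates in patients treated in follow-on courses". Under Exploratory Analyses the plan says "The number and frequencies of second PSA responses in patients treated in follow-on courses will be summarized in tabular format", and that the stratified Mantel-Haenszel test will be "used to compare second PSA response rates between study arms".

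Entry to a follow-on course is set out in Sections 6 and 9:

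- still on trial at month 6: "Patients who have not come off trial at the end of cycle 8 (month 6) will continue to receive pembrolizumab at 3-week intervals" (Section 6);
- "absence of radiographic progression" (Section 9, Cycles 10 and following);
- "evidence of PSA rise (25% increase over value obtained at cycle 9 day 1, and minimum of 2 ng/mL increase" (same place);
- "this occurs prior to cycle 29" (same place).

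Section 11, Analysis Populations, makes ITT the primary population. It does not say how a patient who never starts a follow-on course is to be counted for second PSA response. No section limits how this p-value is to be read.

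**The concern.** Randomization makes the two arms comparable at entry. It does not make comparable the patients who, months later, have met conditions that treatment itself can change. The first two conditions are close to the primary endpoint. The third is measured against a PSA value taken after eight cycles of assigned treatment.

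If Arm 2 delays progression as hypothesised, it brings into its follow-on group some patients whose counterparts in Arm 1 have already left. The two groups then differ in composition because of the treatment. A difference in second PSA response could reflect who was left to be re-vaccinated rather than how well re-vaccination works. Stratifying by institution and prior second-generation AR-targeting therapy balances only what was known at baseline. What is at stake is a p-value that a reader could take as evidence about boosters.

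**Working it through.** **Inputs from the documents.** There are 30 evaluable patients per arm (Section 11, Sample Size and Power Calculation). For Arm 1, "The expected 6-months PFS rate in Arm 1 (pTVG-HP DNA vaccine and Pembrolizumab) in this patient population is 20-30" per cent. For Arm 2 the hypothesis is at least 55%, and the tables cover 50-60%. The plan gives no figure for second PSA response.

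**The plan's own figure.** At 25% vs 55%, one-sided 0.10, the pooled rate is 0.40:

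- SE under the null = √(2 × 0.40 × 0.60 / 30) = 0.1265
- SE under the alternative = √((0.25 × 0.75 + 0.55 × 0.45) / 30) = 0.1204
- Power = Φ((0.30 − 1.2816 × 0.1265) / 0.1204) = Φ(1.145) = 87.4%, as stated.

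All nine cells of the power table reproduce this way, so the design rates are a sound starting point.

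**Size of the two subsets.** Expected number passing the progression condition = 30 × 6-month PFS rate.

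| | Low | Middle | High |
|---|---|---|---|
| Arm 1 | 30 × 0.20 = 6 | 30 × 0.25 = 7.5 | 30 × 0.30 = 9 |
| Arm 2 | 30 × 0.50 = 15 | 30 × 0.55 = 16.5 | 30 × 0.60 = 18 |

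The total is about 21 to 27, and the PSA condition reduces it further. If half of these patients go on to boosters (an assumption), the comparison is 3-4.5 vs 7.5-9 patients.

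**Possible bias against Arm 2.** This is a model with assumed inputs. Let Z be standard normal prognosis. A patient is progression-free at month 6 if ρZ + √(1 − ρ²)·noise exceeds the cut-off that yields 25% (Arm 1) or 55% (Arm 2). The probability of second response has logit = logit(0.30) + g·Z in both arms, so booster efficacy is equal by construction.

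| ρ | g per SD | Arm 1 | Arm 2 | Arm 2 − Arm 1 (points) |
|---|---|---|---|---|
| 0.5 | 0.5 | 37.6% | 34.6% | −3.0 |
| 0.5 | 1.0 | 45.5% | 39.8% | −5.7 |
| 0.8 | 0.5 | 41.8% | 36.8% | about −5 |
| 0.8 | 1.0 | 53.7% | 43.9% | −9.8 |
| 0.5 or 0.8 | 0 | 30.0% | 30.0% | 0 |
| 0.5 | −0.5 | 24.7% | 27.3% | +2.6 |
| 0.8 | −0.5 | 21.1% | 25.0% | +3.9 |

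**Possible bias in favour of Arm 2.** Suppose the 25% who would be progression-free on either arm have a second-response rate of 30%, and the extra 30% held only by Arm 2 have rate p. The observed Arm 2 rate is (0.25 × 0.30 + 0.30 × p) / 0.55:

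- p = 20% gives 24.5%
- p = 30% gives 30.0%
- p = 50% gives 40.9%

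Arm 1 shows 30% throughout. The sign therefore depends on who the extra patients are.

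**Effect on the test.** A variant of the model used ρ = 0.7, intercept −1.5, slope 1, 2 to 10 strata, and 50-80% of progression-free patients going on to boosters. With no true booster difference, the Mantel-Haenszel statistic passed the one-sided 0.10 cut against Arm 2 in 15-17% of simulated trials and in its favour in 6-7%, where 10% each way would be expected. It could not be computed in 0.5-34% of trials, depending on the number of strata and the booster share.

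**The case against.** The strongest reply is that this is one exploratory test, listed as such, with no significance level, power or decision attached. The plan does not claim that the subset is randomized, and it promises a detailed SAP before the final analysis. If the arms do not differ at all, selection acts alike in both and the test keeps its level. All of this stands and keeps the severity low. It does not change what the p-value measures in the case the trial was designed for, where the arms do differ.

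Several stronger readings are tempting, and the documents do not support them:

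- *The test works against the better arm.* A reader might infer this from the usual survivor argument. It needs prognosis to drive both staying progression-free and second response. The documents have no data on that link. The plan's own rationale, broader T-cell activation with two vaccines, would also allow the extra Arm 2 patients to be vaccine-sensitive, which reverses the sign.
- *At most 7.5 vs 16.5 patients can enter.* Those are the counts at 25% vs 55%. The tabulated rates run to 9 vs 18, and more than 60 patients may be randomized.
- *The strata will be mostly empty.* The number of institutions is not given.
- *The result is meant to guide follow-on dosing.* Section 2 says only that second courses can be evaluated, and links future confirmatory trials to clinical activity in general.
- *The objective rules out a comparison.* Its wording asks for rates, but so does the objective for overall objective response, which the plan does compare between arms.

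**Conclusion.** The concern holds as a point about interpretation. Second PSA response is tested between two subsets defined after randomization by events that treatment can affect, and nothing in the documents supplies a randomized denominator or a caution. Under the plan's own hypothesis, about 6-9 vs 15-18 patients pass the progression condition.

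The possible bias is about 3 to 10 points against Arm 2 if the prognosis slope is 0.5-1.0 per SD, the correlation is 0.5-0.8, and boosters work equally well in both arms. It is zero at slope 0 and favours Arm 2 if its extra patients respond well to re-vaccination. Slope, correlation and baseline response rate are all assumptions, so the model shows what could happen and does not predict a result. With the sign unknown, a reader cannot mentally correct the p-value. Severity is low because the endpoint is exploratory and the primary comparison of 6-month PFS does not depend on it.

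**What to change.** In Section 11, Exploratory Analyses, delete the sentence that applies the Mantel-Haenszel test to second PSA response. In its place, report for each arm:

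- the number randomized;
- the number entering follow-on courses;
- the count and rate of second PSA response among those, with a Wilson 95% interval, which is already the plan's method for response rates.

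Add one sentence stating that the arms are not comparable by randomization in this subset.

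Counting every randomized patient without a second response as a failure would restore the randomized comparison, but it answers a different question. In the variant model at 25% vs 55%, with no booster difference and taking all progression-free patients as boosted, it gives 0.25 × 36.8% = 9.2% vs 0.55 × 29.5% = 16.2%. That gap comes only from more Arm 2 patients reaching a booster. It should not be offered as a measure of booster effect.

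The cost is one exploratory p-value from roughly 21 to 27 patients or fewer. Treatment, data collection and the primary analysis do not change.

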12. ADMINISTRATIVE CONSIDERATIONS

x. Specimen Handling

Upon entry into the study, each subject will be assigned a unique identification number. All materials collected on that subject will be labeled with that number only, for reasons of confidentiality, and specimens may be listed with unique codes for individual subjects and obtained at the different time points. Lymphocytes collected will be stored in liquid nitrogen, and sera will be aliquoted and stored at -80° C in the research laboratory of the protocol sponsor ([name]) for immune analyses. Coded stool samples will be initially stored at -80° C in a research laboratory and shipped to [name] laboratory for analysis. No patient identifiers, only coded information, will be transmitted to [name] laboratory.

y. Institutional Review Board

In accordance with federal regulations (21 CFR 312.66), an Institutional Review Board (IRB) that complies with the regulations in 21 CFR 56 must review and approve this protocol and the informed consent form prior to the initiation of the study at each investigator site. In addition, the study cannot be instituted without FDA approval of the vaccine formulations. Finally, the trial will be conducted with adherence to this protocol, following good clinical practice (GCP) guidelines, and in compliance with other applicable regulatory requirements. Any modifications to the protocol must follow the procedure as outlined in Section 16 below.

z. Consent

The Principal Investigator, co-investigators, or their associates must explain verbally and in writing the nature, duration, and purpose of the study and possible consequences of the treatment. Patients must also be informed that they may withdraw from the study at any time and for any reason without jeopardizing their future treatment. In accordance with Federal regulations (21 CFR 312), all patients must sign the IRB-approved consent form.

13. DATA AND SAFETY MONITORING PLAN

A. Definitions

Adverse events (AE) are defined as any unfavorable and unintended sign (including abnormal laboratory finding), symptom or disease temporally associated with a medical treatment or procedure, regardless of whether it is considered related to the treatment or procedure. Adverse events are categorized as definite, probable, possible, unlikely or unrelated in relation to the medical treatment or procedure performed.

AEs include the following:

- 1. An exacerbation, or an unexpected increase in frequency or intensity of a pre-existing condition (other than condition under investigation), including intermittent or episodic conditions.
- 2. Significant or unexpected worsening or exacerbation of the condition/indication under investigation.
- 3. A suspected drug interaction.
- 4. An intercurrent illness.

5. Any clinical significant laboratory abnormality.

An AE does not include:

- 1. Anticipated day-to-day fluctuations of any pre-existing conditions, including the disease under study.
- 2. Signs and symptoms of the disease under study that do not represent a significant worsening or exacerbation.
- 3. Expected progression of the disease under investigation.
- 4. Abnormal laboratory findings that are grade 1 or 2 and are considered clinically insignificant.

Serious adverse events (SAE) are any events occurring that result in any of the following outcomes:

- 1. Subject death
- 2. Life-threatening adverse event
- 3. Inpatient hospitalization or prolongation of existing hospitalization
- 4. Persistent or significant disability/incapacity
- 5. Congenital anomaly or birth defect

A life-threatening event is defined as any adverse event that places the subject, in the view of the investigator, at immediate risk of death from the reaction.

Note: In addition to the above criteria, adverse events meeting any of the below criteria, although not serious per ICH definition, are reportable to the Merck in the same timeframe as SAEs to meet certain local requirements. Therefore, these events are considered serious by Merck for collection purposes.

- Is another important medical event
- Is a new cancer (that is not a condition of the study)
- Is associated with an overdose.

Severity rating/grading scale

Adverse events are classified by organ system and graded by severity according to the current NIH Common Terminology Criteria V. 5, as described in Appendix A. The defined grades use the following general guidelines:

- 0 No adverse event or within normal limits
- 1 Mild adverse event
- 2 Moderate adverse event
- 3 Severe adverse event
- 4 Life-threatening or disabling adverse event
- 5 Fatal adverse event

All adverse events will be recorded from time of treatment initiation through 30 days after the final dose of study treatment, as well as any time after these 30 days for events that are believed to be at least possibly related to study treatment. Please note: SAEs,

regardless of relationship, occurring from the time of consent until 90 days after the final dose of pembrolizumab will be collected and reported as per section E.1.

Appropriate clinical, diagnostic, and laboratory measures to attempt to delineate the cause of the adverse reaction in question must be performed and the results reported. All tests that reveal an abnormality considered to be drug- or vaccine-related will be repeated at appropriate intervals until the course is determined or a return to normal (or pretreatment) values occurs. Information will be recorded as noted above.

B. Disease Oriented Team Meetings

UWCCC site: This study undergoes review of subject safety at regularly scheduled Disease Oriented Team (DOT) meetings where the following are discussed as applicable: number of subjects enrolled, subject treatments given, dose holds/modifications, significant toxicities, response to treatment, and the subjects' overall status. These discussions are documented in the DOT meeting minutes.

C. UWCCC Data and Safety Monitoring Committee (DSMC) Study Progress Review and Oversight

The review of Protocol Summary Reports (PSRs) enables the UWCCC DSMC to assess whether the study should continue, continue with modifications, be suspended, or be closed. Following their review, the UWCCC DSMC will notify the sponsor-investigator of their recommendation and the authority for continuing, modifying, suspending, or closing the protocol is the responsibility of the applicable sponsor-investigator, Principal Investigator, IRB, FDA or other regulatory authority associated with the protocol.

Based on the risk level of this study, as determined by the UWCCC Protocol Review and Monitoring Committee, PSRs must be submitted to the UWCCC DSMC by the UWCCC site on a quarterly basis.

The UWCCC site is responsible for ensuring participating sites enter data used to populate the PSRs in a timely manner into the UWCCC internal database (options may include OnCore or RedCap). This data includes: accrual information, Serious Adverse Events (SAEs), response to treatment, events reportable to IRB (e.g., non-compliance, unanticipated problems).

a. UWCCC DSMC Review of Auditing and/or Monitoring Reports

Reports created through the auditing and/or monitoring activities at all sites are submitted in real-time by the UWCCC site to the UWCCC DSMC. Summary data and/or query reports are submitted in lieu of detailed reports. Following the review of these reports, the committee may issue a request for corrective and/or preventive action(s), protocol suspension, or for-cause audit(s).

b. UWCCC DSMC Review of Non-compliance, Unanticipated Problems, and Other IRB Reportable Events

UWCCC site: Reports of non-compliance, unanticipated problems, and other IRB reportable events are submitted to the IRB of record for the study and to the UWCCC DSMC, via an email to [contact], simultaneously.

Non-UWCCC participating site(s): Reports of non-compliance, unanticipated problems, and other IRB reportable events are submitted to the IRB of record for the site at which the event occurred and to the UWCCC site, via an email to [contact], simultaneously. The UWCCC site forwards the event information to the UWCCC DSMC within 1 business day of receipt.

c. Real-time UWCCC DSMC Review of Serious Adverse Events (SAEs)

The UWCCC DSMC Chair, or designee, reviews all SAEs occurring on the study, regardless of site, to determine if immediate action is required.

UWCCC site: The Principal Investigator (PI), or designee, notifies the following individuals/entities of SAEs as applicable:

- Other investigators involved with the study at the UWCCC
- IRB of record for the study conducted at the UWCCC, per the IRB's reporting requirements
- UWCCC DSMC (Refer to section D)
- Sponsor-Investigator
- UW Institutional Biosafety Officer [[name]: [contact]] (NOTE: IBC is notified only if there is an unexpected potential biohazard exposure)

Non-UWCCC participating sites: The site PI, or designee, notifies the following individuals/entities of SAEs as applicable:

- Other investigators involved with the study at the site
- IRB of record for the study conducted at the site, per the IRB's reporting requirements
- Institutional Biosafety Committee of record for the participating site
- UWCCC site via an email to [contact]

UWCCC site (Sponsor-Investigator or designee): responsibilities are noted in section E

D. Serious Adverse Event Reporting

Serious Adverse Events Requiring 24-Hour Reporting

UWCCC site: All Serious Adverse Events must be reported within 24 hours to the UWCCC DSMC Chair via an email to [contact] within one business day. The OnCore SAE Details Report must be submitted along with other report materials as appropriate (FDA Medwatch Form #3500, UWCCC routing form, UWCCC Sponsor-Investigator Determination Form for FDA Reporting of Safety Events, de-identified supporting documentation available at that time of initial reporting). The UWCCC DSMC Chair reviews the information and determines if immediate action is required. Within 5 calendar days, all available subsequent SAE documentation is submitted electronically, along with a 24 hour follow-up SAE Details Report, to [contact]. This information is entered and tracked in the UWCCC secure, password protected computer network. Refer to the current UWCCC SAE Standard Operating Procedure (SOP) and related documents to facilitate reporting.

UWCCC site (Sponsor-Investigator): Refer to section E for sponsor-investigator responsibilities.

Non-UWCCC participating site(s): All Serious Adverse Events must be reported within 24 hours to the UWCCC site via an email to [contact] and a phone call [contact]) within one business day of the site being aware of the event. The FDA Medwatch Form #3500 Report must be submitted along with other report materials as appropriate (PI assessment form and de-identified supporting documentation available at that time of initial reporting). The UWCCC site will use this information to complete the OnCore SAE Details Report and sends this information, along with the completed UWCCC Sponsor-Investigator Determination Form for FDA Reporting of Safety Events, to the UWCCC DSMC Chair via an email to [contact] within one business day of receipt. The DSMC Chair reviews the information and determines if immediate action is required. If immediate action is required, it is communicated by the UWCCC DSMC Chair to the UWCCC site, who is then responsible for contacting the non-UWCCC participating site. Within 5 calendar days, all available subsequent SAE documentation is submitted electronically, along with a 24 hour follow-up SAE Details Report, to the UWCCC site via an email to [contact]. The UWCCC site sends this information to the UWCCC DSMC Chair via an email to [contact] within one business day of receipt. This information is entered and tracked in the UWCCC secure, password protected computer network.

E. Sponsor-Investigator Responsibilities for SAE Review

The sponsor-investigator (i.e., IND holder), assumes the responsibilities of the study sponsor in accordance with FDA 21 CFR 312.32. In this capacity, the sponsor-investigator reviews all reports of serious adverse events occurring on the study at the UWCCC and non-UWCCC participating sites and makes a documented determination of 1) suspectedness (i.e., whether there is a reasonable possibility that the drug caused the AE); and 2) unexpectedness (the event is not listed in the Investigator's Brochure or is not listed at the specificity or severity that has been observed) in the context of this study. SAE with suspected causality to study drug and deemed unexpected are reported as IND Safety Reports by the sponsor-investigator, or designee, to the following within 15 calendar days unless otherwise designated below:

- FDA
- All participating investigators on the study, and the external global sponsor (if applicable).
- Other oversight committees (NIH OSP)
- Study supporters within 1 day (For additional details, see section E.1):
 - o Merck Co.

Attn: Merck Global Safety, Worldwide Product Safety

[contact]

All fatal or life-threatening SAE that are unexpected and have suspected causality to the study drug will be reported by the sponsor-investigator, or designee, to the following within 7 calendar days unless otherwise designated below:

- FDA
- All participating investigators on the study, and the external global sponsor (if applicable)
- Other oversight committees (NIH OSP)
- Study supporters within 1 day (For additional details, see section E.1):
 - o Merck Co.

Attn: Merck Global Safety, Worldwide Product Safety

[contact]

a. UWCCC Sponsor-Investigator Reporting to the Industry Supporters:

Merck

For purposes of this study, an overdose of pembrolizumab will be defined as any dose of 1,000 mg or greater (≥5 times the indicated dose). No specific information is available on the treatment of overdose of pembrolizumab. In the event of overdose, the participant should be observed closely for signs of toxicity. Appropriate supportive treatment should be provided if clinically indicated.

If an adverse event(s) is associated with ("results from") the overdose of a Merck product, the adverse event(s) is reported as a serious adverse event, even if no other seriousness criteria are met.

If a dose of Merck's product meeting the protocol definition of overdose is taken without any associated clinical symptoms or abnormal laboratory results, the overdose is reported as a non-serious Event of Clinical Interest (ECI), using the terminology "accidental or intentional overdose without adverse effect."

All reports of overdose with and without an adverse event must be reported within 24 hours to the Sponsor-Investigator and within 2 working days hours to Merck Global Safety. (Attn: Worldwide Product Safety; [contact])

For the time period beginning when the study drug is initiated until treatment allocation/randomization, any serious adverse event, or follow up to a serious adverse event, including death due to any cause that occurs to any participant must be reported within 24 hours to the Sponsor-Investigator and within 2 working days to Merck Global Safety if it causes the participant to be excluded from the trial, or is the result of a protocol-specified intervention, including but not limited to washout or discontinuation of usual therapy, diet, placebo treatment or a procedure.

For the time period beginning at treatment allocation/randomization through 90 days following cessation of treatment, or 30 days following cessation of treatment if the participant initiates new anticancer therapy, whichever is earlier, any serious adverse event, or follow up to a serious adverse event, including death due to any cause, whether or not related to the Merck product (pembrolizumab), must be reported within 24 hours to the Sponsor-Investigator and within 2 working days to Merck Global Safety.

Additionally, any serious adverse event, considered by an investigator who is a qualified physician to be related to Merck product that is brought to the attention of the investigator at any time following consent through the end of the specified safety follow-up period specified in the paragraph above, or at any time outside of the time period specified in the previous paragraph also must be reported immediately to Merck Global Safety.

All participants with serious adverse events must be followed to outcome.

SAE reports and any other relevant safety information are to be forwarded to the Merck Global Safety [contact]

A copy of all 7 and 15 Day Reports and Annual Progress Reports is submitted as required by FDA, European Union (EU), Pharmaceutical and Medical Devices agency (PMDA) or other local regulators. Investigators will cross reference this submission according to local regulations to the Merck Investigational Compound Number (IND, CSA, etc.) at the time of submission. Additionally, investigators will submit a copy of these reports to Merck & Co., Inc. (Attn: Worldwide Product Safety; [contact]) at the time of submission to FDA.

Events of Clinical interest

Selected non-serious and serious adverse events are also known as Events of Clinical Interest (ECI) and must be reported within 2 working days to Merck Global Safety. (Attn: Worldwide Product Safety; [contact]).

For the time period beginning when the consent form is signed until treatment allocation/randomization, any ECI, or follow up to an ECI, that occurs to any participant must be reported within 2 working days to Merck Global Safety if it causes the participant to be excluded from the trial, or is the result of a protocol-specified intervention, including but not limited to washout or discontinuation of usual therapy, diet, placebo treatment or a procedure.

For the time period beginning at treatment allocation/randomization through 90 days following cessation of treatment, or 30 days following cessation of treatment if the participant initiates new anticancer therapy, whichever is earlier, any ECI, or follow up to an ECI, whether or not related to Merck product, must be reported within 2 working days to Merck Global Safety.

Events of clinical interest for this trial include:

- 1. An overdose of Merck product, as defined above, that is not associated with clinical symptoms or abnormal laboratory results.
- 2. An elevated AST or ALT lab value that is greater than or equal to 3X the upper limit of normal and an elevated total bilirubin lab value that is greater than or equal to 2X the upper limit of normal and, at the same time, an alkaline phosphatase lab value that is less than 2X the upper limit of normal, as determined by way of protocol-specified laboratory testing or unscheduled laboratory testing.*

*Note: These criteria are based upon available regulatory guidance documents. The purpose of the criteria is to specify a threshold of abnormal hepatic tests that may require an additional evaluation for an underlying etiology.

